4.5. Study Outcome Measures

Primary Outcomes:

- Time to initiation of resistance-pattern appropriate TB treatment from the date of first sputum collection
- Proportion of participants with favourable treatment outcome as defined in section 9.3

Secondary Outcomes:

- Incidence of adverse drug reactions documented during all-oral treatment under operational conditions (cohort 1 and 2)
- All-cause mortality for the duration of treatment and follow-up (cohort 1 and 2)
- Time to sputum (culture) conversion (cohort 1 and 2)
- Prevalence of HR-TB (cohort 1)
- Prevalence of XDR-TB (cohort 2)
- Proportion of participants with BDQ and LZD resistance not eligible for short-course treatment
- Clinical utility and feasibility of TB-MBLA for bacteriological follow-up in DR-TB treatment (assessment of viable bacterial load trajectories in response to treatment) (cohort 1)
- Accuracy and quality of Xpert XDR testing (cohort 1 and 2)
- Additional resistance to new and repurposed drugs (cohort 1 and cohort 2)
- Cost effectiveness (cost per person tested and incremental cost per DR-TB participant timely initiated on appropriate treatment) (cohort 1 and 2)
- Feasibility and acceptability of participant triaging (participant, health care provider and policy makers' perspective) with enablers and barriers for implementing the algorithm (cohort 1 and 2)
- Operational feasibility of Xpert XDR testing (infrastructure and human resource requirements) (cohort 1 and 2)

5. STUDY INTERVENTION

There are 3 study interventions:

1. The Xpert MTB/XDR assay will be used as a diagnostic adjunct to any currently available Nucleic Acid Amplification Tests for drug-resistance detection changes to screen participants. The Xpert MTB/XDR assay will enable prompt identification of the following DR-TB participant categories:
 - a. HR-TB
 - b. Rif mono-resistant TB
 - c. MDR-TB
 - d. Additional fluoroquinolone (FQ) resistance, i.e., pre- XDR TB
2. Early initiation of the most appropriate, evidence-based DR-TB regimen. This will be guided by the TB resistance pattern categorization from the Xpert MTB/XDR diagnostic.

Choice of DR- TB regimen will be determined by:

- a. Best available evidence generated from use of novel regimens as they become available, or
 - b. Current WHO and in-country guidelines (Table 2).
3. In parallel, the TB-MBLA will be used to provide real-time bacillary load monitoring over the course of treatment to assess response to treatment.

Table 2: Current Drug-Resistant TB Treatment Regimen by TB resistance profile and proposed study approach

Current Guidelines on DR- TB treatment	Regimen class	Current Recommended Regimen with Duration (months) by Drug resistance profile per participating country	Proposed All-oral regimen [#]
	HR-TB	RHZE + Lfx (6)	RHZE + Lfx (6) [#]
RR-TB and MDR-TB Short- Course Regimen		
All oral regimen:
 
SA: (4-6)BDQ-Lfx (or MXF)- LZD, INHhd-CFZ-E-Z/ (5) LFX-CFZ-E-Z Nigeria: (4-6)BDQ-MFX-HH-PTO-CFZ-E-Z/ (5)BDQ (2) MFX-CFZ-E-Z Ethiopia:(4-6)AM-MFX-CFZ-HH-PTO-E-Z/ (5)MFX-CFZ-E-Z
 
or
 
Injection-based regimen:
 
(4)AMK-MFX-CFZ- INHhd -PTO-E-Z/(5) MFX-CFZ-E-Z
	BDQ based all-oral regimen [#]
RR-TB; MDR-TB; and PreXDR-TB (Second-line resistance) Long all-oral Regimen* :		
SA: (6)BDQ-LFX-CFZ-LZD/(12)LFX-CFZ- LZD Nigeria: (6)BDQ-MFX-CFZ-LZD/ (12) MFX- CFZ-LZD Ethiopia: (6) BDQ-LFX-LZD-CFZ-CS/(14) LFX- LZD-CFZ-CS
	BPaL [#]
PreXDR-TB (FQ resistance) and XDR-TB# Long Individualised Regimen*:		
SA: (6-8)BDQ-CFZ-LZD-DLM-TRD/(12)CFZ-LZD-TRD-Z- INHhd Nigeria: (6)BDQ-CFZ-LZD-CS/ (12)CFZ-LZD- CS Ethiopia: (BDQ)-(LFX)- (MFX)-(LZD)-(CFZ)-(CS)- (DLM)-(PTO)-(Z)-(AM)-(S)-(PAS)
	BPaL [#]

Abbreviations: HR-TB, Isoniazid Mono-Resistant TB; RR-TB, Rifampicin-Resistant TB; MDR-TB, Multi Drug-Resistant TB; XDR, Extensively Drug-resistant TB, SA, South Africa, LFX, levofloxacin; BDQ, Bedaquiline; MXF, moxifloxacin; LZD, linezolid, INHhd, high-dose isoniazid; CFZ, clofazimine; E, ethambutol; Z, pyrazinamide; PTO, protonamide; DLM, Delamanid; TRD, Terizidone, BPaMz, Bedaquiline -Pretomanid-Moxifloxacin-Pyrazinamide ; BPaL, Bedaquiline -Pretomanid-Linezolid

* Longer regimens recommended when the construction of MDR/RR-TB regimen with 3 group A and 2 group B drugs is not possible due to intolerance to the medicines, acquired additional resistance etc.

Regimen selection based on WHO approved all-oral regimen or the best available evidence-based regimen; once results for proposed BPaMz and ZeNIX Formal amendments will be submitted for review upon consideration of additional regimens for the use in the study

6. INVESTIGATIONAL PLAN

6.1. Selection of study clinical research sites

Countries were selected based on background disease burden of DR-TB and represent a diverse participant population, DR-TB patterns, and laboratory capacities. Clinical research sites (CRS) within countries were selected to ensure sufficient numbers of DR-TB cases to meet recruitment targets. Participants will be enrolled in nine clinical research sites. These are located in South Africa (n=2), Nigeria (n=6) and Ethiopia (n=5) (Figure 2). *Addition of clinical research sites in the study will be based on the ability to meet the enrolment targets for each country. All new clinical research sites will be approved by the in-country local IRB.*

Figure 2: Map of TRIAD Clinical Research Sites in South Africa, Nigeria and Ethiopia

6.2. Selection of Participants

Approximately 4800 participants will be screened across the 13 sites (in South Africa, Nigeria and Ethiopia) to enrol 1280 eligible participants. All presumptive TB patients presenting for diagnosis at the study sites will be approached for screening. Each of the sites will also contribute to the historical cohort as described below.

6.2.1. Selection of cohort 1

880 RR-TB (n=440 in SA, n=220 in Nigeria and n=220 in Ethiopia) participants will be enrolled into Cohort 1. Each participant in cohort 1 will be followed up for the duration of TB treatment and passively thereafter to a maximum of 18 months from TB treatment initiation.

6.2.2. Selection of cohort 2

400 HR participants into Cohort 2 (n=200 in SA, n=100 in Nigeria and Ethiopia). Each participant in cohort 2 will be followed up passively for the duration of TB treatment and passively thereafter to a maximum of six months.

6.2.3. Selection of Historical Cohorts

Each CRS will build a dataset of historical RR-TB participants that were diagnosed and started on treatment within 12 - 18 months prior to starting enrolment of the study at each of the clinical research sites. Clinical and laboratory data from this retrospective cohort will be obtained from treatment registers, participant charts and laboratory databases at each of the clinical research sites. The following data variables will be extracted: date of birth, or age, sex, HIV and ART status, facility or clinic, year and month of treatment, type of DR-TB, certainty of diagnosis (confirmed by DST or presumed, i.e., contact of DR-TB source case or failing adherent first-line TB treatment), disease classification, treatment start date and any bacteriological results on treatment (date, mycobacterial culture, DST and genotypic results), where relevant. Data on all drugs from previous DR-TB treatment regimen, DR-TB Outcomes: cure, completion, default, death, loss to follow up (LTFU) will be abstracted. Historical data will be collected on specially designed case report forms (CRF) and will be subject to routine quality assurance/control QA/QC of data to ensure maximum quality. Bias by time period and by other confounders such as HIV, gender and age, will be controlled for in the analysis. No historical data will be generated for cohort 2, as no routine data on HR-TB is available.

6.3. Participant Inclusion Criteria for cohorts 1 and 2

1. Ambulant adults \geq 18 years of age
2. Newly diagnosed PTB patients receiving less than 5 days of treatment since new diagnosis:
 - a) Cohort 1: < 5 days of DR-TB treatment
 - b) Cohort 2: < 5 days of INH mono-resistant TB treatment preceding study entry for the current TB episode, or
3. Sputum positive (smear and or culture) TB patients classified as failing first line treatment
4. Any currently available Nucleic Acid Amplification Tests for drug-resistance detection changes/assay positive for M.tb infection with:
Cohort 1: at least Rifampicin resistance

- Cohort 2: Rifampicin susceptible co-occurring with INH, fluoroquinolone, ethionamide or aminoglycoside resistance (detected by Xpert XDR) occurring alone or in combination
5. Capacity to provide informed consent
 6. HIV infected and uninfected participants are allowed in the study. Participants already on ART will be allowed in the study provided the ART regimen in use has no contraindications to the proposed TB drug regimen
 7. Willing to have samples collected, stored indefinitely, and used for research purposes
 8. Able to provide reasonable proof of identity (to satisfaction of study team member) at or prior to enrolment

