Study Duration	48 months: study enrolment will occur over 12 -18 months
Sample Size	A total of 1280 participants will be enrolled between 2 prospective study cohorts: Cohort 1 (newly diagnosed DR; rifampicin resistance [RR-TB] participants; n=880) and Cohort 2 (rifampicin sensitive and isoniazid, fluroquinolone and or second line injectable drug (SLID) resistant participants; HR-TB; n=400). Data from a historical cohort (Cohort 3; n=220) of RR-TB participants that accessed DR-TB care at each implementing site over the last 2 years (approximately 24 months) prior to study start.

Study sites	South Africa (n=2), Nigeria (n=6) and Ethiopia (n=5)
Study population	Adult participants (18 years and over) who test positive for pulmonary M.tb with HR-TB or RR-TB will be approached for study participation
Study intervention	Xpert MTB/XDR assay as a triage test to guide early initiation of an appropriate all-oral DR-TB treatment regimen

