- To assess the feasibility of the implementation of the triage and treat approach in routine care

¹ All currently available Nucleic Acid Amplification Tests for drug-resistance detection Positive sputum samples will be screened using Xpert XDR assay until we meet the recruitment target for cohort 2. Thereafter, only RR-TB patients will be screened for cohort 1. Xpert XDR detects resistance to INH, Fluoroquinolones and 2nd Line Injectables

² All eligible patients will provide an additional sputum sample for Xpert XDR testing at screening, if reflex testing on provided sputum sample is not feasible

³ Phenotypic DST to BDQ, Linezolid and Clofazimine will be offered for pre-XDR TB cases as per in-country guidelines

⁴ Choice of regimen will be guided by best available evidence from clinical trials using novel regimen, current WHO and in-country guidelines as described in Table 2

⁵ Primary outcome measures for cohort 1 will be compared to a historical dataset of DR-TB patients diagnosed and treated at the each of the facilities over the last 2 years (approximately 24 months)

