through a multi-step testing cascade. Currently, the front-line molecular diagnostic assay for drug resistance is Cepheid Xpert MTB/RIF or Xpert MTB/Ultra, which detects the presence of *M.tb* bacilli and simultaneously detects RR-TB. Whilst rapidly identifying patients eligible for MDR-TB treatment, the test is limited to the detection of RR only (7, 8). Patients who display RIF resistance receive reflex testing which includes resistance to fluoroquinolones and second-line injectables using standard phenotypic drug susceptibility testing (pDST) and the Hain Line Probe Assays (LPA 1 and 2), which detect resistance to isoniazid, rifampicin, fluoroquinolones and second-line injectable agents (9). Drug susceptibility testing (DST) for all other drugs is conducted using phenotypic testing methods. However, following a rapid diagnosis by Xpert MTB/RIF or Xpert MTB/Ultra, all follow-on testing is conducted at a regional laboratory thereby increasing the turn-around times for providing a comprehensive resistance profile. Furthermore, these DST methods have several limitations. Although LPA testing can be rapidly performed on sputum samples, LPAs require specialised laboratory facilities, longer turnaround time and are associated with a high indeterminate rate (~30%) in smear-negative patients (10). Phenotypic DST (pDST) techniques require approximately 4-6 weeks and result interpretation are compounded by issues with the established critical drug concentrations used to predict resistance and poor performance for certain drugs such as ethionamide and pyrazinamide. Currently, DR-TB patients are initiated on empiric treatment, which is modified as DST results become available, resulting in a 4-6-week delay in initiation of appropriate treatment. As a result of this sub-optimal testing cascade, many patients may receive a limited number of effective drugs in the regimen, increasing the risk of amplifying drug resistance and ongoing transmission of DR-TB (3). A further challenge which hinders the diagnosis and treatment of DR-TB is the lack of susceptibility testing for isoniazid resistance by assays available at the point where the patient enters the care cascade, i.e. Xpert MTB/RIF, Xpert MTB/RIF Ultra, or the Truenat assays. As a consequence, isoniazid mono-resistant TB patients (HR-TB; i.e. patients who display INH resistance in the absence of RIF resistance) are not appropriately diagnosed. This sub-set of patients receive standard DS-TB treatment, thereby increasing the risk of amplifying drug resistance (11).

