4. STUDY DESIGN, AIMS AND OBJECTIVES

4.1. Study Design

The study is a Prospective Pragmatic Cohort Study with a before-and-after study design

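### The historical comparator has two conflicting time windows, and its extraction list omits dates that the time-to-treatment endpoint needs

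*Protocol*

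**What the plan says.** **Window.** Section 6.2.3 reads: "Each CRS will build a dataset of historical RR-TB participants that were diagnosed and started on treatment within 12 - 18 months prior" to the start of enrolment at each clinical research site. Table 1 (Sample Size row) describes the same cohort as patients in care at each implementing site "over the last 2 years (approximately 24 months"), and counts back from a point worded "prior to study start". Footnote 5 of the Study Summary, which names the comparator for the primary outcomes, refers to a "historical dataset of DR-TB patients diagnosed and treated at the each of the facilities over the last 2 years (approximately 24 months") and gives no anchor date.

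**Endpoint 1.** Section 4.5 defines it as "Time to initiation of resistance-pattern appropriate TB treatment from the date of first sputum collection". Section 9.2 repeats the two end points of the interval and requires the same interval to be measured in the historical cohort.

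**Extraction list.** Section 6.2.3 lists the variables to be taken from registers, charts and laboratory databases. The dated items are "treatment start date and any bacteriological results on treatment (date, mycobacterial culture, DST and genotypic results"). Year and month of treatment, type of DR-TB, certainty of diagnosis, the drugs used and the outcome category are also listed. A first sputum collection date is not, and neither is a date on which the regimen was changed or became appropriate.

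**Standard care.** Section 2.1 says that "DR-TB patients are initiated on empiric treatment, which is modified as DST results become available", so a first start date and an appropriate-regimen start date can differ.

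**The concern.** Section 4.1 calls the study a "Prospective Pragmatic Cohort Study with a before-and-after study design". The historical cohort is therefore the only comparator for either primary endpoint, and which records are pulled and which dates are copied from them determine what the primary comparisons mean.

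The window conflict touches both endpoints. Each site builds its own dataset, and section 6.2 counts 13 sites. If some follow 6.2.3 and others Table 1, controls will come from different periods at different sites, in a field where section 2.1 describes rapid changes in regimens.

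The missing dates touch endpoint 1 only. Without the first sputum date the interval has no starting point in controls. Without a date for the appropriate regimen, a site that enters the listed treatment start date may record the empiric start instead. That would make the historical interval look shorter than the one defined in section 9.2.

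**Working it through.** The plan gives no figure for this point that could be reproduced. The power statement in section 9.1 is not in question here, and nothing below depends on it.

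**Step 1: the windows side by side.**
- Section 6.2.3: 12 to 18 months, counted from the start of enrolment at each site.
- Table 1: about 24 months, counted from study start.
- Footnote 5: about 24 months, no anchor stated.

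The lengths disagree whichever anchor is meant. The 6.2.3 wording is also ambiguous in itself. It can mean the last 12 months, the last 18 months, or the six-month interval lying between 12 and 18 months back.

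**Step 2: how far the windows differ.** Assume that patients accrue evenly over the 24 months. The share of a 24-month pool outside the 6.2.3 window is 1 − (width in months)/24.
- Last 18 months: 1 − 18/24 = 25%.
- Last 12 months: 1 − 12/24 = 50%.
- Interval from 12 to 18 months back (6 months wide): 1 − 6/24 = 75%.

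If study start and a site's own start are m months apart, the two anchors also shift that site's window by m months. The protocol gives no value for m. These shares are not converted into numbers of patients, because Table 1 does not make clear whether its historical n=220 is a total or a per-site figure.

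**Step 3: dates needed against dates listed, endpoint 1.**
- Starting point, first sputum collection (sections 4.5 and 9.2): not on the list. The only dated bacteriology is described as taken on treatment, whereas the first diagnostic sputum would normally precede treatment.
- End point, start of the regimen that fits the resistance pattern (section 9.2): one treatment start date is listed. It is the needed date if the first regimen already fitted the pattern. It is not if the regimen was changed after DST, and no change date is listed.

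Of the two dates needed, one is absent for every control and the other is available only for those whose first regimen was already appropriate.

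**Step 4: can the error be sized?** No. The share of historical patients whose regimen was changed is not given, nor is the time between the two starts in these sites' own records.

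**The case against.** The strongest reply is that section 6.2 sends the reader to 6.2.3 for the historical cohort, so 6.2.3 governs and Table 1 is only a summary. The list is also not the whole data source: 6.2.3 names charts, registers and laboratory databases and a purpose-built form, and section 9.2 states the required interval. Much of this is fair. It makes the repair small, but it does not remove two different window lengths from current text, or put the missing dates on the list. What a protocol may leave to its analysis plan does not include dates that were never abstracted.

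Several stronger readings are tempting and are not supported:
- **Two definite anchors.** Table 1 refers to each implementing site, so its study start can be read as the start at that site. The wording needs aligning, but the conflict that is certain is in the window lengths.
- **Endpoint 1 is lost for all controls.** The end-date gap is confined to patients whose first regimen was later changed, and the first sputum date may well be in the laboratory sources already named. The fault is that the list does not ask for it.
- **A bias of four to six weeks.** Section 2.1 gives that delay as background. Subtracting it from the literature medians in section 9.1 would assume that both use the same definition, which the protocol does not show.
- **Presumed cases contaminate the controls.** Recording certainty of diagnosis is not a rule admitting presumed cases. It is the field that allows them to be set aside, and that rule can sit in the analysis plan.
- **Time-period bias cannot be addressed.** Year and month of treatment are extracted, so partial adjustment for calendar time is possible. The promise in 6.2.3 is worded too firmly, but no size can be attached to that.

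**Conclusion.** The point holds in two parts. First, the sole comparator for both primary endpoints has two window lengths in current text, 12 to 18 months against about 24, and the shorter one has three possible readings. The gap is 25%, 50% or 75% of a 24-month pool under even accrual. This is window arithmetic resting on that assumption, and it says nothing about the direction or size of any bias. Second, for endpoint 1 only, the extraction list followed as written does not supply the interval that section 9.2 requires: the starting date is missing, and the end date is uncertain for patients whose regimen was modified. No number of days is claimed. Both parts should be settled before historical extraction, or by amending the form if extraction is under way, because neither can be repaired at the analysis stage.

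**What to change.** - State one window and one anchor (start of enrolment at each site, or study start) in identical words in Table 1, footnote 5 and section 6.2.3. Give it as a from-to interval so that it has only one reading.
- Add to the historical case report form the first sputum collection date, the DST, LPA and genotypic result dates, and the start date of the resistance-appropriate regimen, with regimen-change dates.

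The cost is a few more retrospective fields from sources already named, and some dates will be missing from registers. A shorter window gives fewer controls closer in time; a longer one gives more controls from an older period.

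Two minor notes. The recorded certainty-of-diagnosis field can be used to keep the primary comparison to laboratory-confirmed RR-TB. The sentence on time-period bias should acknowledge that adjusting for calendar time in a before-and-after design leaves residual secular trend.

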6.4. Participant Exclusion Criteria

Study participants will be excluded if one or more of the following conditions apply:

1. Has a known severe allergy to any of the BPaL component drugs
2. Has DST showing infection with a strain resistant to any of the component drugs
3. Has TB meningitis, other central nervous system TB, or TB osteomyelitis; or
4. Is pregnant or breastfeeding
5. Is unable to take oral medications
6. Persons with any other medical condition, precluding study participation based on investigator judgement
7. Any co-existing condition that in the opinion of the attending clinician renders the participant unsuitable for participation in the study
8. Co-enrolment in other interventional research studies

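### Cohort 1's eligibility criteria are not applied to the historical comparator, which likely biases favourable outcome towards the intervention and leaves time to treatment non-comparable

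*Protocol*

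**What the plan says.** Protocol section 6.2.3 sets the rule for the historical cohort: "Each CRS will build a dataset of historical RR-TB participants that were diagnosed and started on treatment" within a stated period before enrolment. It gives no age limit, disease site, diagnostic test or exclusion. Its extraction list includes "certainty of diagnosis (confirmed by DST or presumed, i.e., contact of DR-TB source case or failing adherent first-line TB treatment", so presumed cases are expected.

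The prospective criteria are scoped differently. The heading reads "6.3. Participant Inclusion Criteria for cohorts 1 and 2". The list opens with "Ambulant adults" aged 18 or over, refers to pulmonary TB, and requires a positive nucleic acid amplification test, with "Cohort 1: at least Rifampicin resistance". Section 6.4 excludes study participants who, among other things, have component-drug resistance, are pregnant or breastfeeding, or cannot take oral drugs. It also lists "Has TB meningitis, other central nervous system TB, or TB osteomyelitis; or" and "Any co-existing condition that in the opinion of the attending clinician renders the participant unsuitable for participation in the study". Section 6.5 adds a late exclusion for resistance to the BPaL drugs found after enrolment. Nothing carries these rules over to the historical cohort.

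The stated remedy is "Bias by time period and by other confounders such as HIV, gender and age, will be controlled for in the analysis". Section 9.2 adds multivariable analysis without naming covariates.

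**The concern.** The study is non-randomised and before-and-after, so the credibility of both primary comparisons rests on the two groups being alike in everything except the triage strategy. Here one group passes a filter and the other does not. Several of the filtered conditions plausibly carry a worse prognosis: being non-ambulant, central nervous system or bone TB, resistance to regimen drugs, and conditions a clinician judges unsuitable. Removing such patients from one side only raises the success proportion in cohort 1 even if the strategy does nothing.

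Regression adjustment is a weak answer for two reasons. It cannot use variables that were never abstracted, and it has no cohort 1 patients with whom to compare a type of patient that cohort 1 excludes.

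**Working it through.** **1. Which criteria the extracted data can mirror**

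- Already extracted under 6.2.3: age or date of birth, sex, HIV and ART status, type of DR-TB, certainty of diagnosis, disease classification, DST and genotypic results. Restriction on age, confirmed rifampicin resistance and recorded component-drug resistance is possible, as is restriction on disease site if the classification records it.
- Not on the list: ambulatory status, pregnancy or breastfeeding, ability to take oral drugs, comorbidity. These can be neither restricted on nor adjusted for.
- Cannot be mirrored even in principle: the judgement-based exclusions (6.4, criteria 6 and 7).

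**2. The plan's own figure**

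Section 9.1 states 80% power for 74% versus 85% with 220 per site, allowing 15% loss. The significance level is not stated; two-sided 0.05 is assumed. With 220 × 0.85 = 187 prospective against 220 historical, power is 78.2%; with 220 against 220 it is 81.8%. The stated figure is broadly reproduced. The problem is comparability, not sample size.

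**3. Size of the bias if the stated rate describes all historical patients**

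Let S be overall historical success, f the share who would fail cohort 1's criteria and e their success. Success among eligible historical patients is (S − f·e)/(1 − f), and the spurious gain is this minus S. S comes from section 9.1: 74% (short bedaquiline-based regimen) or 63% (average). The protocol gives neither f nor e; both are assumed.

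| f | e | S = 74%: eligible (gain) | S = 63%: eligible (gain) |
|---|---|---|---|
| 5% | 50% | 75.3% (+1.3) | 63.7% (+0.7) |
| 10% | 40% | 77.8% (+3.8) | 65.6% (+2.6) |
| 20% | 40% | 82.5% (+8.5) | 68.75% (+5.75) |
| 20% | 30% | 85.0% (+11.0) | 71.25% (+8.25) |

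Example: (0.74 − 0.10 × 0.40)/0.90 = 0.70/0.90 = 77.8%.

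**4. Size if 74% describes eligible patients instead**

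Historical success is then h = (1 − f) × 0.74 + f·e. With no true effect, the chance of a significant result in the intervention's favour is Φ((d − 1.96·se0)/se1). Here d = 0.74 − h, and se0 and se1 are the pooled and unpooled standard errors. Two sizes are shown: 187 versus 187, and 748 (880 × 0.85) versus 220.

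- f = 5%, e = 50%: d = 1.2 points; 4.5% or 5.6%
- f = 10%, e = 40%: d = 3.4 points; 11% or 17%
- f = 20%, e = 40%: d = 6.8 points; 30% or 51%
- f = 20%, e = 30%: d = 8.8 points; 46% or 72%

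The nominal rate is 2.5%.

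**5. Time to appropriate treatment**

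Two features pull in opposite directions.

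- Cohort 1 must be positive on a molecular test; historical patients need not be. Table 6 shows how much the diagnostic route matters: in the Johannesburg series the medians are 17 days (Xpert-based), 38 (line probe) and 81 (phenotypic). Slower routes among historical patients would lengthen their times.
- Historical patients must have started treatment. Dropping never-starters and pre-treatment deaths tends to shorten historical times. Presumed or very ill patients may also have been started quickly.

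The documents give no figures to weigh one against the other.

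**The case against.** The strongest reply is that much of this needs no new data. Age, disease classification, certainty of diagnosis and resistance results are already extracted, the confounder list is open-ended, and a statistical analysis plan could define a restricted comparator. That stands for those criteria. It does not stand for ambulatory status, pregnancy, ability to take oral drugs and comorbidity, because no later plan can restrict on data that were not abstracted.

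The size is also fairly contested. Both f and e are assumptions. The 11-point figure occurs only at the extreme corner of both and at the 74% baseline; at the 63% average the range stops at about 8 points. Restricting on a poorly recorded field could also introduce selection by record completeness, which the fix has to avoid.

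Three stronger readings are tempting and not supported:

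- A reader might infer that both primary comparisons favour the intervention. For time to treatment the direction is not fixed (step 5).
- A reader might call the historical cohort unselected, or assume it contains children, extrapulmonary cases and pregnant women. It is selected on RR-TB and treatment start, and section 6.2.3 is silent on those groups. Apart from presumed cases, which the extraction list names, the text fails to exclude them; it does not say they are in.
- A reader might list the critically ill as excluded from cohort 1. No criterion says so, and section 10.2 expects that some participants may be critically ill. Only ambulant status, inability to take oral drugs and the judgement-based exclusions bear on severity.

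**Conclusion.** The concern holds as a comparability defect. Followed as written, the protocol compares a cohort filtered by sections 6.3 to 6.5 with one selected only on RR-TB, diagnosis and treatment start. For favourable outcome the bias is likely towards the intervention. This rests on the excluded patients having poorer outcomes, which is plausible but not quantified in the protocol. Under the assumed inputs the spurious gain ranges from under 1 point to the whole planned 11-point difference, and the protocol contains nothing to show where in that range the truth lies. For time to appropriate treatment the groups are not comparable, but no direction can be claimed. The planned adjustment for period, HIV, gender and age does not resolve either problem.

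**What to change.** - In section 6.2.3, state that historical records must meet the 6.3 and 6.4 criteria that records allow: age 18 or over, pulmonary disease, confirmed rifampicin resistance, no central nervous system or bone TB, and no component-drug resistance where recorded. These use fields already listed.
- Add ambulatory or inpatient status at treatment start, pregnancy or breastfeeding, and ability to take oral drugs to the historical case report form. Apply them where recorded, and do not drop a record only because they are missing.
- Make this set the comparator for both primary endpoints. Report the unrestricted set, and alternative handling of missing status, as sensitivity analyses.
- Treat the 6.5 late exclusions alike in both groups, or keep those participants in the primary analysis.
- Log how many patients are excluded under 6.4 criteria 6 and 7, and state that these cannot be mirrored.

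The cost is a paragraph of protocol text, three more items to abstract, and a somewhat smaller historical set. Some imbalance from the judgement-based exclusions and unrecorded comorbidity will remain and should be acknowledged.
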